Preliminary steps: Participants who are invited back for a group alcohol drinking session will be asked not to eat for 3 hours pre-arrival. Alcohol drinking will occur either in a bar lab or other room located at Yon Hall North in Ben Hill Griffin Stadium at the University of Florida campus. At around 3:45pm, participants will be brought to the bar or simulated laboratory for the session via study-provided transportation: either a professional service such as taxi or Uber or a UF-owned automobile driven by a UF employee (Table 2). However, if a participant lives within a 0.5 mile radius of the research facility they may walk to the facility rather than being driven. At the end of the session, these participants may be walked home by study staff. Upon arrival at 4pm, BrAC (must=.00%) and urine tests will be repeated (Table 2). Participants registering a BAC > 0.00% or with a positive urine test that leads to exclusion will be dismissed immediately and provided transportation directly home by the study. At this appointment, participants will receive an abbreviated version of the instructions on how to use the app and its value (see below). Participants will also complete baseline self-reports and the cued go/no-go task on the app. Before the alcohol administration, participants may be asked to wear the BACTrack Skyn. Each session will be scheduled with 3 people each assigned to a different app, but if 1 cannot participate, the session may still occur. While it is our preference that this appointment occur at 4pm just before the rest of the drinking session activities, if a participant's schedule does not permit it, the 4pm activities may also be scheduled earlier in the day on the day of the session or the day before. In the case of an appointment the day before, the urine drug and pregnancy test will still occur on the day of the session. Payment for this appointment will be \$20 via cash card and will be transmitted on the day of the appointment.

Instructions: The day of the group session participants will be given a brief review of the instructions that were given to them at their individual drinking sessions. Participants will be asked to not share their results on the app with the other participants. Study staff will explain to participants that to incentivize fast, accurate performance (Fig. 2a), they will get \$.10 each

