Normal probability plots will be reviewed to assess normality and need for transformations. Paired samples *t*-tests will be used to confirm an effect of initial dose on CGNG inhibition errors but not RT. Our analytic strategy will resemble 3 past studies. The main method will be multiple regression with study condition and sex as predictors. Baseline variables that differ significantly by condition will be covaried.

Outcome 1a will be BAC during self-administration. Because we will not interrupt alcohol self-administration with BrAC readings, we will calculate peak estimated BAC (eBAC) based on number of alcoholic drinks, time elapsed, weight and sex. eBAC was sensitive to differences in consumption between study conditions in a prior study conducted by [name]. Results will be BrAC-confirmed after the 1-hr free-drinking period. Though not the main focus, we will test 2-way interactions of study condition by RT and inhibition errors post-alcohol to see if more inhibition failures under alcohol predict self-administration. Regressions will be confirmed using multilevel models (MLM) in Mplus with random effect of group (people completing a drinking session together) and other predictors as fixed effects. Since participants will be randomized to different apps, we do not expect strong intra-class correlations, which should result in similar findings in regression and MLMs. In our in-progress study, no group level effects have emerged. A similar strategy will be used for 1b (alcoholic drinks self-administered).

Primary Aim 2 will entail comparisons of alcoholic drinks consumed per occasion between the 2 weeks participants will use vs. not use the app in the 4-week field period post-drinking session. We will retain study condition as a predictor (effects of lab-assigned condition are not hypothesized here) and a random group effect while adding app use vs. non-use period as a within-subjects effect in MLM. ANOVA will compare usability and acceptability ratings at the end of the drinking session and 4-week field period across app conditions. For mediation (Secondary Aim), we will test for indirect effects of app condition on self-administration via perceived impairment using MacKinnon’s products of coefficients approach with bootstrapped confidence intervals (CIs). This approach accounts for non-normality of the product of

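### The main Aim 1 analysis leaves out the drinking group, although each session is a block with one person per app; any positive residual ICC makes its standard errors too wide

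*Combined protocol and SAP*

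**What the plan says.** Section 6, Data analyses, names the primary method: "The main method will be multiple regression with study condition and sex as predictors". For Outcome 1a it then adds: "Regressions will be confirmed using multilevel models (MLM) in Mplus with random effect of group", where a group is the people who share a drinking session. Outcome 1b is to be handled in a similar way.

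Two supports are offered for expecting little similarity within groups. The first is an inference from the design: "Since participants will be randomized to different apps, we do not expect strong intra-class correlations", "which should result in similar findings in regression and MLMs". The second is empirical: "In our in-progress study, no group level effects have emerged". No ICC, interval or number of groups goes with the second.

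The composition of a group is set out under Group Alcohol Drinking Session, Preliminary steps: "Each session will be scheduled with 3 people each assigned to a different app, but if 1 cannot participate, the session may still occur". Section 7 likewise describes two or three participants per session.

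The power calculation (Sample, power & effect size) uses d=.89, alpha .025 for each of two comparisons and 99 completers, and arrives at .90. It contains no group term.

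**The concern.** The similarity that matters for the standard error is what remains between co-drinkers after app and sex are in the model. It would come from sharing a room, a pace and a social setting during an hour of free drinking. The protocol takes that setting seriously enough to measure bonding within the group (Assessments, Social bonding). Different app assignments keep app from being confounded with session. They do nothing to make three people who drink together behave more independently.

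Since app varies inside the session, a session effect is common to all three apps and cancels from every app contrast. A regression without the group leaves that shared variation in its error term. Its intervals are then wider than the design requires, and its tests reject less often than the nominal level under the null. If the two planned models differ, the one named as the main method is the one with the less suitable error term, and the plan does not say which result stands.

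**Working it through.** **Inputs from the documents.** 33 per condition, 99 in total; d=.89; alpha .025 per comparison; sessions of three with one person per app, two permitted. Two-sided testing is assumed because the plan does not state sidedness.

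**Inputs assumed.** Residual ICC of 0, .1, .2 or .3, because the documents give none. A smaller effect of d=.60 for illustration; it is not in the documents.

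**1. The plan's own figure.** In SD units the standard error of a difference between two arms of 33 is sqrt(2/33) = .2462, so the noncentrality is .89/.2462 = 3.615. At two-sided .025, power is .904 (t, 64 df), .908 (t, 96 df) or .915 (normal). The stated .90 is reproduced. One-sided .025 would give about .95, which does not match.

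**2. Complete triads.** With 33 sessions, each holding one person per app:
- true variance of an app contrast = 2(1−ICC)/33
- variance reported by the regression ≈ 2/33
- ratio of reported to true SE = 1/sqrt(1−ICC)

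Real type I error at nominal .025 is the chance that a standard normal exceeds, in absolute value, the critical value times that ratio. The range uses critical values 2.277 (t, 96 df) and 2.241 (normal).

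| Assumed ICC | True SE | Reported SE | Overstatement | Real type I error |
|---|---|---|---|---|
| .1 | .2335 | .2462 | 5% | .016–.018 |
| .2 | .2202 | .2462 | 12% | .011–.012 |
| .3 | .2060 | .2462 | 20% | .006–.007 |

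**3. Sessions of two.** If every session loses one member at random, an average of 16.5 of the 49.5 sessions contain both apps of a given contrast, with 33 people per arm. The covariance of the two arm means is 16.5·ICC/33², so the true variance is (2/33)(1−ICC/2) and the ratio is about 1/sqrt(1−ICC/2): 1.026, 1.054 and 1.085. An exact calculation of the covariance gives 1.026, 1.053 and 1.084, that is about 3%, 5% and 8%.

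**4. Power, complete triads, two-sided .025.** Regression: Φ[(d − 2.277×.2462)/true SE]. Group model: noncentral t with (33−1)(3−1) = 64 df and noncentrality d/true SE. Example at ICC .2 and d=.89: regression Φ[(.89−.5606)/.2202] = Φ(1.496) = .933; group model with noncentrality .89/.2202 = 4.04 gives .957.

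| Assumed ICC | d=.89: regression vs group model | d=.60: regression vs group model |
|---|---|---|
| 0 | .910 vs .904 | .56 vs .56 |
| .1 | .921 vs .932 | .57 vs .61 |
| .2 | .933 vs .957 | .57 vs .67 |
| .3 | .945 vs .977 | .58 vs .73 |

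Simulation of 33 triads per trial agrees with these figures to within about one point. It also shows how the models would disagree: at d=.60 and ICC .2, the group model alone reached significance in about 9% of trials and the regression alone in essentially none.

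**5. The other direction.** The regression's SE is too narrow only if the ICC is negative. At −.2 the real type I error would be about .041.

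**The case against.** - **The group is in the plan.** A reader might infer that clustering is ignored. It is not: the random-group model is specified for 1a, a similar strategy applies to 1b, and Aim 2 keeps a random group effect. What stands is narrower: which model decides, and what happens if they differ.
- **The ICC may be near zero.** The remark about the in-progress study is the only empirical information in the documents. It is unquantified, and the plan itself says that study's methods are not identical, so it is weak support, but nothing in the documents contradicts it. At ICC 0 the regression is very slightly better (.910 vs .904).
- **Power is adequate.** A reader might infer that Aim 1 is underpowered or its error rate inflated. Neither holds under positive ICC. At d=.89 the loss is 1 to 3 points and power stays above .90; type I error is below nominal.
- **Blocks are a scheduling target.** Randomization precedes the individual session, and groups are formed afterwards by availability. Sessions of two shrink the effect without reversing it.
- **The sentence is true of raw similarity.** Different treatments within a group do lower the unadjusted ICC. If the experimental app differed from both controls by .89 SD, a residual ICC of .10 would leave a within-group mean square of .90 + .89²/3 = 1.164 against a between-group mean square of .90 + 3×.10 = 1.20, and a raw ICC of (1.20−1.164)/(1.20+2×1.164) ≈ .01. But the raw ICC does not govern the SE once condition is in the model. With complete triads and adjustment for condition alone, the two models also give the same point estimates; it is the error bars that differ.

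**Conclusion.** The point holds as one of efficiency and clarity. The decision analysis for 1a and 1b omits a blocking factor that the schedule creates, and the reason offered for expecting it not to matter does not bear on the residual ICC. The cost is precision: tests are conservative and intervals too wide, by 5% to 20% with complete triads and about 3% to 8% with sessions of two, over an assumed ICC range of .1 to .3. At the planned effect the consequence is small. It becomes material, at 4 to 15 points of power, if the true effect is nearer the assumed d=.60.

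The documents do not support reading this as a source of false positives, nor as evidence that co-drinkers will in fact resemble each other strongly. The size rests on an ICC they do not report.

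**What to change.** In Data analyses:
- Make the already-planned model with a random group effect the decision analysis for 1a and 1b, and state small-sample degrees of freedom for it.
- Keep the regression on condition and sex as the sensitivity check, so that it is clear which result stands if they differ.
- Remove the inference from different apps to low ICC, or correct it to say that within-session assignment prevents confounding of app with group.
- Report the estimated residual ICC and the number of sessions of two and three. The ICC will also help plan the larger study that this one is meant to inform.

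The cost is mainly wording. The plan names Mplus but says nothing about degrees of freedom, so that detail must be added and the software checked for it. With an ICC near zero the loss is negligible. With about 33 groups the group variance may be estimated at zero, in which case the result is essentially the regression.

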This study (N=99) will test an app giving in-the-moment feedback on impaired inhibitory control as an adjunct to an existing, web-based intervention (US-THRIVE) addressing general drinking patterns, based on M.I.⁵⁴⁻⁵⁶⁻²¹. US-THRIVE was linked to significant drinking reductions in a sample with low baseline motivation¹⁶. This new app will give in-the-moment feedback comparing pre- and post-drinking RT and inhibition errors, referring to evidence that poor CGNG response relates to poor simulated driving and willingness engage in risky behavior. After feedback, the app will offer advice on slowing drinking and other options (e.g., a taxi). The experimental app—derived from a larger app (RWJF #73293, PIs: [name]/[name])—will be compared to standard (trial-by-trial RT and error information only) and control versions (no information) without feedback. After US-THRIVE, heavy drinking young adults will be randomized to 1 of the 3 apps. They will use this app initially and learn about the relevance of alcohol’s effects on CGNG. They will then attend an individual alcohol drinking session where they will be dosed to .06% BAC, followed by app use. After completion of the first session they may be asked to return to the research facility on a different day to take part in a group alcohol drinking session where they will be dosed to .06% BAC in groups of 3, followed by app use, then 1-hr when they can self-administer alcohol up to .12%^{57, 58}. They will use the app post-drinking with incentives for fast, accurate performance⁴⁴ and learn their number of errors and fast + correct responses. Performance decrement should motivate subsequent app use. Similar to R21AA023368 (PI: [name]), for 4 weeks post-session, all participants will use the experimental app for 2 weeks in real drinking occasions and not use it the other 2 weeks. Due to the COVID-19 pandemic participants may be asked to complete just the 4 week field use portion of this study.

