 In a pilot study ($N=76$, 67% female, 25% non-white, M age= 43[$SD=14$]), consultant [name] compared a standard CGNG with the app version in his current study, which required 3 min., on average. This app version of the CGNG will be elaborated in the proposed study. Reaction times (RTs) in the app and computer versions were highly correlated ($r=.69$, $p<.01$). The trials in the app version were divided into thirds

[figure not shown]

Figure 2b

and mean RTs were correlated to evaluate reliability. RTs among each third were correlated between .89-.95, indicating strong reliability. Correlations of inhibition errors on the computer version and errors on the app were lower, $r=.28$ ($p=.015$). This is not surprising as CGNG errors are infrequent when sober. This is actually an advantage as it enhances sensitivity to alcohol effects. Given the promising findings and extensive literature on the CGNG⁴⁵⁻⁵¹, we are confident the app version will be sensitive to alcohol. [name] included a description of the app in a preliminary study of young adult drinkers ($N=23$). Participants rated the likelihood they would use the app 5.1 ($SD=1.3$) on a 1-7 scale. In a recent web survey of young adults in FL ($N=72$), [name] found 66% of heavy drinkers reported scores ≥ 3 on a 0-10 scale, indicating agreement they would like to use an app to help reduce drinking, suggesting high interest and a degree of motivation.

Summary: These studies show feasibility; young adults' motivation to use moderate drinking apps even if they take several minutes; our experience with relevant methods; external validity of the CGNG; and reliability and validity of the app version of the CGNG. Thus, the CGNG is a good choice for in-the-moment intervention.

5. Specific Aims

Primary Aim 1: Compare effects of a smartphone app providing feedback on impaired inhibitory control to 2 control conditions on BAC (Aim 1a) and number of alcoholic drinks self-administered (1b) during a 1-hour free drinking period in a naturalistic bar lab that occurs immediately after a fixed alcohol dose targeting BAC= .06%.

Primary Aim 2: In a 4-week period post-session, compare, within-subject, number of drinks per occasion during 2 weeks when participants use the app during actual drinking situations vs. 2 weeks when they will not use the app. Also test app satisfaction including number of times used and likelihood of future use.

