Participants will be otherwise healthy men and women between the ages of 21-25 who frequently engage in heavy alcohol use. This study will test an app based on the cued go/no-go (CGNG) task giving in-the-moment feedback on impaired inhibitory control as an adjunct to an existing, web-based intervention (US-THRIVE) targeting general drinking patterns using M.I. principles. This new app will give in-the-moment feedback comparing pre- and post-drinking RT and errors, referring to evidence that poor CGNG response relates to poor simulated driving and willingness to engage in risky behavior. After feedback, the app will offer advice on slowing drinking and other options to avoid harm (e.g., a taxi). The experimental app—derived from a larger app (Robert Wood Johnson Foundation grant #73293, PIs: [name]/[name])—will be compared to standard (trial-by-trial RT and error information only) and control versions (no information) without feedback. After US-THRIVE, heavy drinking young adults will be randomized to 1 of the 3 apps. After initial use of their randomized app, they will then be dosed to .06% BAC during an individual session in a naturalistic lab, followed by app use. After this initial session, on a separate day, participants will attend a group session including 2 other participants. During this group session; they will again be dosed to .06% BAC, followed by app use, then 1-hr when they can self-administer alcohol up to .12%. There will be at least one day between the individual and group sessions and the goal will be for the individual and group session to occur within 7 days of each other. For 4 weeks post-session, all participants will use the experimental app for 2 weeks in real drinking occasions and not use it the other 2 weeks. Participants completing both the laboratory alcohol administration and field testing components of the study can earn up to \$450 during the course of study participation. Participants may also be invited to complete only field use of the app due to the COVID-19 pandemic or because they cannot physically come to the study location on campus. Among these participants, some will be invited to complete the four-week field use period as described above (i.e., 4 weeks total, 2 weeks with app access, 2 weeks with not and a brief daily questionnaire each day for the 4 weeks). Maximum possible payment for those chosen to complete only the field use period will be \$310. A small subset (up to n= 12 participants) will be selected to complete an ecological momentary assessment based field period of 10 days in which participants will be prompted multiple times per day to either use the app or to complete a brief questionnaire. Maximum payment for those completing the ecological momentary assessment will be \$200. We anticipate enrolling 208 participants, of whom 109 will be eligible with a target of 99 individuals completing the study.

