Preliminary steps: Participants will be asked not to eat for 3 hours pre-arrival. Alcohol drinking will occur in a bar lab located at Yon Hall North in Ben Hill Griffin Stadium at the University Florida campus. Participants will be brought to the bar or simulated laboratory for the session via study-provided transportation: either a professional service such as taxi or Uber or a UF-owned automobile driven by a UF employee. However, if a participant lives within a 0.5-mile radius of the research facility they may walk to the facility rather than being driven. These participants may be walked home by study staff after the end of the alcohol drinking session. Upon arrival, BrAC must=0.00% and urine tests will be repeated. Participants registering a BAC > 0.00% or with a positive urine test that leads to exclusion will be dismissed immediately and provided transportation directly home by the study. Participants will complete US-THRIVE, an efficacious, brief, web intervention based on M.I. (i.e., personalized feedback on drinking patterns, behavioral strategies, alcohol facts and resources). Before the alcohol administration, participants may be asked to wear the BACTrack Skyn alcohol wristband monitor, which looks like a fitness tracker or wristwatch and can detect alcohol as it evaporates through the skin. Prior to the session, they will be randomized to 1 of the 3 app conditions. The randomization procedure will be managed by a study staff member/collaborator without direct participant contact. Staff working with participants will not know app assignment.

Instructions: After participants learn their app condition, they will view a presentation on the CGNG and how to use their assigned app. They will be told the app is based on a cognitive game and that they will use it 3 times. They will learn that the task is relevant to real-life as moderate amounts of alcohol affect task success and poor performance has been linked to driving problems and risky decisions. [name] has used similar instructions relating alcohol to task performance and pay^{65, 66} and seen a range of alcohol use in lab drinking sessions.

Alcohol administration steps: After completing US-THRIVE and using the app, the participant will be given vodka mixed drinks targeting a BAC of .06% based on sex, height, and weight divided into three parts. The participant will have 10 minutes to complete each drink and after

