We will collect data for 4 weeks as people engage in usual drinking. The app will be programmed to deploy the CGNG, give related feedback and offer advice for 2 of the 4 wks (counterbalanced), enabling within-subject comparison of alcohol use with vs. without the main component app. The app will prompt 3 times on typical drinking days. Participants can set the app to prompt on other days also. After CGNG and feedback, participants report perceived impairment, the number of standard drinks they have consumed to that point and the extent to which they want and would like more alcohol. During the 2-weeks when the app does not deploy the CGNG task and feedback, participants will answer the questions only. Each morning for the 4 weeks, the app will prompt recording of number of drinks and time spent drinking the prior day. Data collected by the app will not be visible after it is submitted so minimal information about participants will be visible in the app if the phone is stolen, lost, "hacked" or in some other way made visible to another person. Even though task performance and self-report responses are no longer visible after submission we suggest that all participants password protect their phone, and change the auto lock to 1 minute so that the application cannot be accidentally accessed by anyone other than the study participant. Participants completing only the field use period will attend a baseline appointment, which can be held remotely via a password-protected UF Zoom meeting. During this baseline appointment participants will be walked through how to download the smartphone application, and shown how to use the app. They will be asked to use the app during the appointment to gather baseline data, and will then be pinged again later that evening or the following morning to use the app again. Compensation for this appointment will be \$10. Following their baseline appointments participants will be asked to attend an orientation appointment where they will receive their randomized version of the smartphone application. They will receive \$10 for this appointment. Participants completing lab sessions will complete these appointments in the course of their session participation and receive the same

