not use the experimental app. No study condition effect is hypothesized, thus the focus will be on within-subjects comparison. As such, assuming $\alpha=.05$ at 90% power, we can detect an effect of .33 (small-to-medium). The secondary aim of testing the indirect effect of app condition on drinking via perceived impairment will require the largest sample size as it entails tests of between group differences and tests of indirect effects are underpowered relative to tests of direct effects. In a Monte Carlo simulation, assuming small-to-medium correlation (.35) between perceived impairment and drinks self-administered (DV), power to detect an effect of the IV (study condition) on the mediator and an effect of the mediator on the outcome was $>.90$ and power to detect an indirect effect was .80 with 33 per condition (N=99 total).

7. Possible Discomforts and Risks

Potential risks in this study were identified in accordance with the recommended guidelines on ethyl alcohol administration in human experimentation put forth by the National Advisory Council on Alcohol Abuse and Alcoholism (2005) and two reviews on this subject (Dolinsky & Babor, 1997; Wood & Sher, 2000). Steps taken to minimize these risks were also developed in accordance with these documents.

Alcohol consumption: A number of medical conditions could potentially be worsened by acute alcohol administration (e.g., liver disease, cardiac abnormality, pancreatitis, diabetes, neurological problems, and gastrointestinal disorders). As a result, participants with such medical problems as revealed by a medical history taken during the in-person screening will be excluded from the study.

Alcohol self-administration in a research study by individuals who are severely alcohol dependent as evidenced by current withdrawal or a history of withdrawal may pose a risk to their health and safety. Alcohol self-administration in a research study by individuals who are seeking treatment for alcohol use disorder or who have recently engaged in intensive treatment for alcohol dependence may compromise their efforts to reach or to maintain abstinence or moderate levels of alcohol use.

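### The Primary Aim 2 model has no calendar-period or order term for its counterbalanced on/off weeks; adding one is a nearly free safeguard for power, not a correction of the stated .33

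*Combined protocol and SAP*

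**What the plan says.** Primary Aim 2 (5. Specific Aims) is to "compare, within-subject, number of drinks per occasion during 2 weeks when participants use the app during actual drinking situations", set against two weeks without it. Under Post-session field use, the order of the weeks is varied across participants: "The app will be programmed to deploy the CGNG, give related feedback and offer advice for 2 of the 4 wks (counterbalanced". That section does not say whether the two on-weeks form one block or alternate with off-weeks, or how participants are allocated to an order.

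Under Data analyses, the Aim 2 model keeps study condition "and a random group effect while adding app use vs. non-use period as a within-subjects effect in MLM". In that sentence the word period means the app-on or app-off condition, not the first or second half of the four weeks. No section names a term for calendar period, week or order.

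Under Sample, power & effect size, the Aim 2 figure at alpha .05 and 90% power is "we can detect an effect of .33 (small-to-medium". The Overview gives the sample as eligible participants "of whom 109 will be eligible with a target of 99 individuals completing the study".

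**The concern.** Counterbalancing makes any general change in drinking over the four weeks cancel, on average, between the two orders. It does not remove that change from the individual on-off differences. Someone with the app first has a difference shifted one way by the drift, and someone with the app second has it shifted the other way. If the model ignores order, that spread counts as error. The usual analysis of a counterbalanced two-condition design therefore includes period.

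Drift is plausible, though not documented. Lab participants complete a web intervention before the field period ("Participants will complete US-THRIVE, an efficacious, brief, web intervention based on M.I"), and the Background says of it that "US-THRIVE was linked to significant drinking reductions in a sample with low baseline motivation". Self-monitoring runs throughout: "Each morning for the 4 weeks, the app will prompt recording of number of drinks and time spent drinking the prior day". If drinking falls or rises as the weeks pass, the precision of a primary-aim contrast is at stake. Should the orders become clearly unequal, its freedom from bias is at stake too.

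**Working it through.** **Inputs.** From the documents: N = 99 completers out of 109 eligible; alpha .05; power .90; detectable effect .33. Assumed, because the documents are silent: two-sided testing; drift P, the mean change in drinking from the first to the second two weeks, at .25, .5 or .75 SD of the within-person on-off difference (.75 is more than twice the target effect, so an upper end); two solid blocks, unless stated otherwise.

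**1. The plan's own figure.** Normal approximation: (1.960 + 1.282)/√99 = .326. Paired t with 98 df: .329. The one-sided version gives about .296 and does not match. So .33 reproduces as a two-sided test on 99 person-level differences.

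**2. Person-level differences.** Scale the differences to SD 1 within order. Their mean is δ + P in one order and δ − P in the other. With near-equal orders and no order term, the variance becomes about 1 + P². The effect detectable at 90% power is then (t·√(1 + P²) + 1.282)/√99, with t = 1.9845:

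- P = .25: (1.9845 × 1.031 + 1.282)/9.950 = .334
- P = .5: (1.9845 × 1.118 + 1.282)/9.950 = .352
- P = .75: (1.9845 × 1.250 + 1.282)/9.950 = .378

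Simulated results at an effect of .329 follow. They average over both drift directions and over random loss of 10 from 109, starting at 55:54.

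| Drift P | Power, no period | Type I error, no period | Power, with period | Type I error, with period |
|---|---|---|---|---|
| .25 | .89 | .044 | .90 | .05 |
| .5 | .85 | .03 | .90 | .05 |
| .75 | .78 | .017 | .90 | .05 |

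With the period term (97 df, orders 50:49) the detectable effect is still .329.

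**3. Unequal orders.** Without the term, bias = P × (n₁ − n₂)/99.

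- 52:47 (about 95% of random losses are no more unequal than this): P × 5/99 = .013/.025/.038 SD. Power is .86/.79/.66 if drift runs against the app and .91/.90/.88 if it runs in its favour. With the term it is .90 either way.
- 59:40: P × 19/99 = .048/.096/.144 SD, with type I error .07/.11/.15.

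**4. Occasion-level model with a random participant intercept.** Here the error is pooled over occasions, and drift enters only through the person-by-condition part. With k = 5 occasions per condition, the residual df are 99 × 10 − 99 − 1 = 890, of which 98 carry the drift. The residual variance is therefore multiplied by about 1 + (98/890)P² = 1.007/1.028/1.062, instead of 1 + P². Simulated power without the period term is about .90/.90/.89, and type I error about .05/.05/.04. With k = 3, power is about .90/.90/.88. Five occasions is in line with the entry criterion of at least 12 drinking days in 30 (12 × 14/30 = 5.6 per two weeks). This assumes that the app effect does not vary between people. With a random app-use slope, or one mean per person per condition, the results of step 2 return.

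**5. Layout.** If single weeks alternate, the same linear drift contributes P/2, and person-level power is .90/.89/.87. In an on-off-off-on layout, linear drift cancels within each person.

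**The case against.** The strongest reply is that the plan specifies a multilevel model on drinks per occasion, not a paired t on 99 differences, and that in the plainest such model the loss is about a point of power even at the largest assumed drift. This stands: the power loss depends on a modelling choice that the plan does not state.

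The grounds for drift are also modest. A reduction from the web intervention that is already in place by week 1 affects both halves alike, and becomes drift only if it keeps changing. Daily recording is the same in all four weeks. No document gives a drift figure. This stands too, and is why every drift value here is an assumption.

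Finally, the Aim 2 description is a short summary, and a period term might be added in practice. That is possible, but nothing in the text says so, and counterbalancing alone does not take drift out of the error.

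Three stronger readings are tempting and are not supported:

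- **That the missing term biases Aim 2 or invalidates its test.** With near-equal orders, bias is essentially nil and type I error stays at or below about .05. Only clearly unequal orders inflate it, and the stated counterbalancing makes those unlikely.
- **That .33 is wrong, or holds only if drift is absent or modelled.** It reproduces, and at .25 SD drift without the term the detectable effect is .334.
- **That the analysis set is left open for participants who do only the field period.** Data analyses places Aim 2 after the drinking session, and the power section describes the 99 as having completed the lab session, so both point to lab completers.

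**Conclusion.** The Aim 2 model omits calendar period and order from a design that counterbalances them. The omission is harmless to validity while the orders stay near-equal. Its cost ranges from nothing to about 12 points of power (.90 to .78). The upper end requires two solid blocks, drift of .75 SD and an analysis on person-level differences or with a random app-use slope. At .25 SD the person-level loss is about one point. In an occasion-level random-intercept model with about five occasions per condition, it is about one point or less at every drift tried.

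This is a worthwhile and nearly free improvement, not an error in the stated .33. Nothing here addresses carryover of app learning into off-weeks, which a period term would not remove.

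**What to change.** Add fixed effects for period (first versus second two weeks, or week number if weeks alternate) and for order to the Aim 2 multilevel model. Fit it with the participant level that a within-subjects effect already implies.

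The cost is a line of text and about one degree of freedom, and the detectable effect stays at about .33. Allocation, visits and data collection do not change. The app's programmed on/off weeks, together with the login dates and times described under Smartphone app use in section 7, already give period and order.
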